10.5 Management of toxicity and hypersensitivity reactions

Patients should be evaluated for history or risk of hypersensitivity to the active substance, to any of the ingredients listed in section 6.1 of the SMPC, or to β -lactam antibiotics (e.g. penicillins, cephalosporins). Flucloxacillin is contra-indicated in patients with a previous history of Flucloxacillin-associated jaundice/hepatic dysfunction. Participants with previous allergic reaction to penicillin will for this reason be excluded from the trial. Participants who experience signs of post-administration reactions should be managed as per local NHS guidance and any suspected reactions should be reported to the CTR.

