All participants will receive the standard wound care advice that they would normally receive as part of routine NHS standard of care with possible signs and symptoms of SSI explained to them. Participants will also be given clear written and pictorial material (designed in collaboration with our Patient Partners), including what to look for to identify a wound infection. Participants will be reassured that prompt treatment will be available for any participants with SSI. All participants will be given contact details (including out-of-hours where applicable) of their local recruiting centre and will be advised to contact their local recruiting centre if they have any concerns about wound infection or side effects from the antibiotic tablets to arrange a face-to-face review. Financial assistance will be provided towards participant transport costs for the face-to-face review (if required) to support people on low incomes to participate in the trial, in line with recommendations from the NIHR INCLUDE Socioeconomic Disadvantage Framework (55).

We recognise that some participants with symptoms of wound infection may seek medical advice locally from another health care professional e.g., GP, out-of-hours GP, Emergency Department however participants will be given emergency contact details of their local recruiting site and will be asked to contact them if an SSI is suspected. Suspected SSIs will be assessed at local recruiting site and if an SSI is confirmed, participants will be requested to provide a wound swab, and again 7 days later if infection has not responded to treatment, as per CDC criteria (16).

IRAS: 1009425

Follow-up procedures

Participants will be provided with a patient diary to capture their subjective journey through the trial, and record any symptoms of SSI and notes on their general health, to aid in completion of follow-up assessments by the research team.

All participants will be telephoned by the local research team around days 5-10, days 15-20 and at day 30 (+/-7 days) following surgery to ask about any concerns about wound infection or side effects.

Participants will be encouraged to identify a nominated support person (e.g. a family member) to assist them with trial-related activities, such as wound photos and completing questionnaires, which will support the inclusion of digitally excluded populations and participants with cognitive impairment/ impaired capacity.

SSI diagnosis

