11.2 Follow-up

Day 30 (+/- 7 days) and 3 month (+/- 7 days) follow ups will be completed by telephone/email/post by the research nurses.

30-day follow-up:

- Adverse events
- New antibiotics
- SSI telephone assessment with face-to-face wound review if patient/clinician concern
- Wound swabs if SSI diagnosed
- Participant QoL EQ-5D-5L Questionnaire and Bluebelle WHQ questionnaire.

IRAS: 1009425

- Time to return to normal work/ activity
- Resource use (related to wound complications including SSI including report of hospital visits/stays)
- Qualitative interviews (optional n=40)

3-month follow-up:

- Participant QoL EQ-5D-5L Questionnaire
- Time to return to normal work/ activity
- Resource use (related to wound complications including SSI including report of hospital visits/stays)

Around three attempts will be made to contact the participant at each follow-up by telephone. If it is not possible to contact participants, the participant's support person (if nominated) may be contacted as an alternative. If all contact attempts are unsuccessful, a questionnaire booklet may be posted to the participants for them to complete and return.

The follow-up period will end 3 months (+/- 7 days) after the last recruited participant has been randomised and initiates medication (at completion of their 3-month follow-up assessment).

GYMRU Caerdydd a'r Fro
NHS
WALES University Health Board Bwrdd Iechyd Prifysgol Caerdydd a'r Fro

	Assessment	Source Data	Data type/Measure	Screening & Baseline	Day 5-10	Day 15-20	Day 30 (+ 7/7)	3 months (+ 7/7)	Responsible for Data Collection	Justification
1	Eligibility Assessment	Screening log, CRF, documented in medical notes	Inclusion /Exclusion criteria	X					Qualified medical professional with delegated responsibilities	Eligibility
2	Informed consent	Consent form, documented in medical notes	Informed consent	х					Qualified medical professional with delegated responsibilities and site research team who are appropriately qualified, experienced and delegated by the PI	Consent
3	Demographics	CRF	- Age - Sex - Gender - Ethnicity	Х					Site research team	Baseline
4	Contact details	CRF	- Contact details (inc. Postcode) - Alternative Contact details - GP Contact details - NHS number	Х					Site research team	Trial Management
5	Medical history	CRF, documented in medical notes	Co-occurring conditions	Х					Participant Reported/ Site research team	Baseline

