6	Skin /lesion examination	CRF, documented in medical notes	Skin surgical site	X	(X)	(X)	(X)		Qualified medical professional with delegated responsibilities	Baseline
7	Concurrent/ new medication	CRF, documented in	- Current medication - Antibiotic use	Х	Х	Х	Х	Х	Participant Reported/ Site research team	Baseline and Fidelity of

CYMRU CHARU Caerdydd a'r Fro
NHS WALES University Health Board

	Assessment	Source Data	Data type/Measure	Screening & Baseline	Day 5-10	Day 15-20	Day 30 (+ 7/7)	3 months (+7/7)	Responsible for Data Collection	Justification
		medical notes								intervention
8	Performance status/ Frailty score	CRF	- ECOG Performance Status- Rockwood Clinical FrailtyScore	Х					Participant Reported/ Site research team	Baseline
9	Randomisation	CRF	Randomised medication	Х					Site research team	Randomisation
10	Dispensing of trial drugs	CRF, documented in medical notes	Trial medication	Х					Site research team	Baseline and Fidelity of intervention
11	Adverse event assessment	CRF, documented in medical notes	- SAEs - SARs	X	Х	X	X		Site research team	Pharmacovigilance
12	SSI assessment (telephone)	CRF	Primary outcome		х	х	X		Qualified medical professional with delegated responsibilities and site research team who are appropriately qualified, experienced and delegated by the PI	Primary outcome
13	SSI assessment (face-to-face)	CRF, documented in medical notes	Primary outcome		(X)	(X)	(X)		Qualified medical professional with delegated responsibilities	Primary outcome
14	Wound swab	CRF, documented in medical notes	Antimicrobial resistance analysis - MALDI- Tof - MIC - EUCAST disc diffusion		(X)	(X)	(X)		Qualified medical professional with delegated responsibilities	Secondary outcome
15	Health- related Quality of Life	CRF	- EQ-5D-5L - Time to return to normal activity	Х			X X	X X	Participant reported	Secondary Outcomes
16	Resource use	CRF	- Health economic data - Resource use				Х	X	Participant reported / Site research team	Secondary outcome

Bwrdd lechyd Prifysgol Caerdydd a'r Fro Cardiff and Vale University Health Board

	Assessment	Source Data	Data type/Measure	Screening & Baseline	Day 5-10	Day 15-20	Day 30 (+ 7/7)	3 months (+ 7/7)	Responsible for Data Collection	Justification
17	'Selfi- wound' (requested)	CRF	- Feasibility		Х				Participant reported / Site research team	Secondary outcome
18	Bluebelle WHQ	Questionnaire	- Response rates - Validity				Х		Participant reported	SWAT

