14.5 Reporting procedures

14.5.1 Participating Site Responsibilities

The PI (or delegated medically qualified doctor from the trial team) should sign and date the SAE CRF to acknowledge that he/she has performed the seriousness and causality assessments. Investigators should also report SAEs to their own health boards or trust in accordance with local practice.

A completed SAE form for all events requiring immediate reporting should be submitted via fax or email to the CTR within 24 hours of knowledge of the event. A separate form must be used to report each event, irrespective of whether or not the events had the same date of onset.

The participant will be identified only by trial number, month, and year of birth and initials. The participant's name (or any other personal identifiers) should not be used on any correspondence.

It is also required that sites respond to and clarify any queries raised on any reported SAEs and report any additional information as and when it becomes available through to the resolution of the event. Additionally, CTR/ pharmaceutical companies may request additional information relating to any SAEs/ SARs and the site should provide as much information as is available to them in order to resolve these queries.

Serious Adverse Event (SAE) email address:

[contact]

SAE [contact]

SAEs should be reported from time of randomisation, and up to, and including 30 days after the participant receives their dose of the IMP. SARs (such as long-term side effects of trial treatment under investigation) should continue to be reported until the end of follow up as defined in the protocol.

SAEs should be graded using the NCI Common Terminology Criteria for Adverse Events (CTCAE) Version 5.0.

IRAS: 1009425

An SAE form should contain at least the minimum information:

• Full participant trial number.

- An Adverse Event / Adverse Reaction.
- Trial intervention.
- A completed assessment of the seriousness, and causality as performed by the PI (or another appropriately medically qualified doctor registered on the delegation log).

If any of these details are missing, the site will be contacted, and the information must be provided by the site to the CTR within 24 hours.

Except SSIs, no other AEs should be reported on the CRF as Flucloxacillin is a marketed product with a significant amount of safety data available.

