14.5.2 The CTR responsibilities

Following the initial report, all SAEs should be followed up to resolution wherever possible, and further information may be requested by the CTR. Follow up information must be provided on a new SAE form.

The CTR should continue reporting SAEs until 30 days after the participant receives their last dose of the investigational medicinal product. Serious adverse reactions should continue to be reported until the end of follow up.

Once an SAE is received at the CTR, it will be evaluated by staff at the CTR and sent to the Chief Investigator (or their delegate) for an assessment of expectedness.

Investigator reports of suspected SARs will be reviewed immediately and those that are identified as SUSARs are reported to the sponsor, IMP supply company, MHRA and REC.

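### Serious adverse reactions are reportable to 3 months, but the last scheduled adverse-event enquiry is at day 30, so late reactions are not actively sought

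*Protocol*

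**What the plan says.** Section 14.5.1 sets two reporting windows for sites. For serious adverse events in general, "SAEs should be reported from time of randomisation, and up to, and including 30 days after the participant receives their dose of the IMP". For serious adverse reactions the window is longer: "SARs (such as long-term side effects of trial treatment under investigation) should continue to be reported until the end of follow up". Section 14.5.2 gives the trials unit the same duty: "Serious adverse reactions should continue to be reported until the end of follow up". Section 20 puts the end of follow-up at 3 months from randomisation.

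The schedule of enquiry is set out in three other places:

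- Section 11, under follow-up procedures, has the local team telephone every participant at about days 5-10, days 15-20 and day 30 "following surgery to ask about any concerns about wound infection or side effects".
- Section 11.2 lists adverse events among the 30-day items. Its 3-month list holds only the EQ-5D-5L, resumption of usual work or activity, and "Resource use (related to wound complications including SSI including report of hospital visits/stays").
- Table 2, row 11, "Adverse event assessment", gives SAEs and SARs as its data type. It is marked at baseline, days 5-10, days 15-20 and day 30. The 3-month cell is empty.

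**The concern.** The protocol deliberately keeps the SAR window open for about two months after general SAE reporting has closed, and gives long-term side effects as its example. No scheduled step looks for such events in that period.

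A SAR can be recognised only once a serious event has become known to the site and its causality has been assessed (section 14.3). Up to day 30 the calls bring serious events to light. After day 30 nobody is scheduled to ask, and a serious event not judged related is no longer reportable. Recognition then depends on the participant, or someone acting for them, making the link to a single dose taken weeks earlier. The feasibility study population averaged 77 years (section 9.2), and the trial admits people who lack capacity to consent (section 9.4.1), so unprompted reporting is a weak basis for that period.

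At stake is how an empty list of late SARs can be read in the annual safety report (section 14.8) and in SUSAR reporting (section 14.6): it could mean that no reactions occurred, or that nobody asked.

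**Working it through.** The protocol gives no figure for this point, so there is none to reproduce. The check compares the two windows and then counts days.

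**Side by side**

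| | Runs to | Source |
|---|---|---|
| SAE reporting | 30 days after the dose | 14.5.1 |
| SAR reporting | End of follow-up, 3 months | 14.5.1, 14.5.2, 20 |
| Side-effect telephone calls | Day 30 | 11, follow-up procedures |
| Adverse-event item in the visit lists | Day 30 | 11.1, 11.2 |
| Table 2 row 11 (SAEs, SARs) | Day 30 | Table 2 |

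The empty 3-month cell is unlikely to be a fault of text extraction: row 7 (medication) carries marks in all five columns, and the narrative list in section 11.2 omits adverse events at 3 months as well.

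**Inputs for the day count**

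- Day-30 contact: day 30, window plus or minus 7 days, so day 23 to day 37 (section 11.2).
- 3-month contact: taken as day 91, window plus or minus 7 days, so day 84 to day 98 (section 11.2).
- Assumptions: 3 months = 91 days; surgery takes place on the day of randomisation, so that both clocks start together.

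**Formula**

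Share of the window without scheduled enquiry = (day of 3-month contact − day of day-30 contact) / day of 3-month contact.

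**Results**

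- Nominal: (91 − 30) / 91 = 61/91 = 67%.
- Smallest (late day-30 contact, early 3-month contact): (84 − 37) / 84 = 47/84 = 56%.
- Largest (early day-30 contact, late 3-month contact): (98 − 23) / 98 = 75/98 = 77%.

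These are shares of time, not of reactions. The protocol has no data on when serious reactions would occur, so the share of reactions missed cannot be calculated from it.

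**The case against.** The strongest reply is that a reporting duty may properly outlast active enquiry. The duty runs from knowledge of the event (sections 14 and 14.5.1), so a site that learns of a SAR on day 60 and reports it within 24 hours has complied. The trial is classed as Type A (section 6.1), the drug is marketed and given once, and light safety collection is a stated choice. This stands: there is no formal contradiction, and a reader who infers that sites cannot meet the SAR rule goes further than the text allows.

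Other stronger readings also fail:

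- **That most late reactions will be lost.** No figure supports this. Passive routes exist: participants are told to contact the site about side effects, with no end date given (section 11); medication is recorded at 3 months (Table 2, row 7); and patient records are a permitted data source (section 11.1). None is a question about serious events, but each could bring one to light.
- **That the harm outcome is compromised.** The adverse-event outcome in section 5.5 covers 30 days from surgery, which the schedule covers.
- **That a 3-month safety bound is invalid.** Zero events in 190 exposed participants would give an upper 95% limit of about 3/190 = 1.6%, and one could argue that it holds only to day 30. But the protocol nowhere promises a 3-month safety estimate.
- **That late liver reactions are the expected loss.** Section 10.5 mentions a "previous history of Flucloxacillin-associated jaundice/hepatic dysfunction" only as a contraindication and says nothing about time of onset.
- **That a non-wound admission will certainly not be asked about.** Section 11.2 ties the resource-use item to wound complications, but section 5.5 places hospital visits and stays outside that bracket, and section 16.2 says the instrument is still to be developed.

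What the reply does not remove is that the protocol names a class of late serious event that it wants reported and schedules no step to find it.

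**Conclusion.** The point holds as a gap in ascertainment. For about two thirds of the stated SAR window (the 61 of 91 days counted above), serious reactions are not actively solicited. The facts come straight from the protocol; the percentages rest on the two timing assumptions stated with the day count.

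The consequence is limited to SAR and SUSAR surveillance after day 30. The primary outcome and the 30-day adverse-event outcome are unaffected. The absence of enquiry does not show that reactions will occur after day 30 or that those occurring will be missed. It means only that an absence of late SARs would be weak evidence. Given how little it costs to close, the gap is worth closing.

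**What to change.** Preferred: in Table 2, mark row 11 at 3 months for SARs, and add to the 3-month list in section 11.2 one question on any serious illness or hospital admission of any cause since the day-30 contact. Because that contact may be by telephone, email or post, the question should appear in every version. Sites would assess causality of positive answers under section 14.3 and report those judged to be SARs.

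Cost: one question at a contact that already takes place, a table edit in the next amendment, and a few unrelated events for sites to screen.

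Alternative: if active enquiry after day 30 is not wanted, reconcile the passages by stating in sections 14.5.1 and 14.5.2 that SARs after day 30 are spontaneously reported only, so that readers of the safety reports know how that period was observed. This costs only wording, but leaves ascertainment as it is.

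The health-economic resource-use item need not be widened to all causes; the single safety question is enough.

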5.2 Secondary objectives

- To assess the adverse events of a single dose (1g) of oral flucloxacillin.
- To investigate antibiotic resistance in infected wounds.
- To evaluate the cost effectiveness of oral flucloxacillin and no antibiotic treatment.
- To evaluate participants' and clinicians' views on oral antibiotics in preventing wound infection.
- To investigate the feasibility of 'Selfi-wound' photos.
- To validate the WHQ for SSI assessment in skin surgery.

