5.5 Secondary outcomes measures

• The number of participants with adverse events within 30 days of surgery using the Medical Dictionary for Regulatory Activities.

- Antibiotic resistance to clinically relevant antibiotics will be evaluated in isolates from participants' wounds at diagnosis of SSI and after 7 days if no response to treatment. This will be assessed by a central microbiology laboratory (Public Health Wales).
- Health-related QoL measured by EQ-5D-5L questionnaires at baseline, 30 days and 3 months.
- Time to return to normal activity/work at 30 days and 3 months.
- Resource use (related to wound complications including SSI) and cost of hospital visits/stays at 30 days and 3 months.
- Qualitative process evaluation assessing implementation and acceptability of oral antibiotics including facilitators and barriers.
- Feasibility of 'Selfi-wound' photos as measured by the number of participants who were able to successfully take and transmit an image of their wound images via the online system.
- Validation of WHQ remote use for SSI assessment via SWAT.

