14.1 Definitions

Table 3: Definitions of Adverse and Serious Adverse Events and Reactions.

Term	Definition

Adverse Event (AE) Adverse Reaction (AR)	Any untoward medical occurrence in a participant or clinical trial participant administered a medicinal product and which are not necessarily caused by or related to that product. Any untoward and unintended response in a clinical trial participant to an investigational medicinal product which is related to any dose administered to that participant.					
Serious Adverse Event (SAE)	 Any adverse event that - Results in death Is life-threatening* Required hospitalisation or prolongation of existing hospitalisation** Results in persistent or significant disability or incapacity Consists of a congenital anomaly or birth defect Other medically important condition*** 					
Serious Adverse Reactions (SARs)	Any SAE occurring in a clinical trial participant for which there is a reasonable possibility that it is related to the IMP at any dose administered.					
Suspected Unexpected Serious Adverse Reactions (SUSARs)	A SAR, the nature and severity of which is not consistent with the Reference Safety Information (RSI) for the IMP.					

^{*}Note: The term 'life-threatening' in the definition of serious refers to an event in which the trial participant was at risk of death at the time of the event or it is suspected that used or continued used of the product would result in the subjects death; it does not refer to an event which hypothetically might have caused death if it were more severe.

[figure not shown]

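### The protocol promises an adverse-event outcome but bars non-serious events other than SSI from the CRF, so the outcome as worded cannot be produced until the sections are reconciled

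*Protocol*

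**What the plan says.** Several sections of the protocol point towards collecting adverse events of any severity.

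- Section 5.2 gives the secondary objective: "To assess the adverse events of a single dose (1g) of oral flucloxacillin".
- Section 5.5, like the Synopsis, gives the outcome: "The number of participants with adverse events within 30 days of surgery using the Medical Dictionary for Regulatory Activities". Neither is restricted to serious events.
- Section 14.1 defines an adverse event broadly, including events "which are not necessarily caused by or related to that product", and defines serious events as a separate, narrower class.
- Sections 11.1 and 11.2 list adverse events as an assessment at baseline, days 5-10, days 15-20 and day 30. Section 11.1 says that the data collected go into the trial database.
- Section 11 (Follow-up procedures) has the site telephone every participant at the three post-surgery time points "to ask about any concerns about wound infection or side effects". Section 9.1 describes a daily diary that also covers side effects.
- Section 10.5 asks that suspected reactions after dosing be reported to the CTR, with no seriousness threshold.

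Two places point the other way.

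- Section 14.5.1: "Except SSIs, no other AEs should be reported on the CRF". The reason given is that flucloxacillin is already marketed, with a large body of safety data.
- Table 2, row 11, gives the content of the adverse event assessment as SAEs and SARs only.

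Serious events have their own form and window in Section 14.5.1: "SAEs should be reported from time of randomisation, and up to, and including 30 days after the participant receives their dose of the IMP".

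**The concern.** A stated recording rule removes the data that a stated objective and outcome need. This is a conflict inside the current protocol text, not a detail that can be left to the analysis plan.

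Harm matters to this trial's question. The background section says that no randomised trial has studied the benefits and harms of oral flucloxacillin in this setting, and the lay summary gives avoidable side effects as a reason for the trial. Section 15.3 asks the monitoring committee to weigh secondary outcomes and safety data when it considers the non-binding futility boundary. If the rule in Section 14.5.1 is applied, the non-serious part of that safety evidence is missing from the CRF at the interim and at the end.

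Sites also face instructions that they cannot all obey: assess adverse events at each contact, ask about side effects, report suspected reactions to the CTR, and enter no adverse event other than SSI on the CRF. Different sites may resolve this differently, which would make the counts hard to interpret.

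**Working it through.** **Step 1. Which events have a permitted route into the trial data?**

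| Event type | Within the outcome in 5.5? | Route under 14.5.1 and Table 2 row 11 | Text pointing the other way |
|---|---|---|---|
| SAE, SAR | Yes | SAE form | none |
| SSI | Not stated | CRF (primary outcome) | none |
| Non-serious suspected reaction | Yes | None on the CRF | 10.5 (report to CTR); 11.1, 11.2 |
| Other non-serious adverse event | Yes | None on the CRF | 11.1, 11.2 |

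Section 14.1 defines a SAR as an SAE with a reasonable possibility of relation to the drug. Row 11 of Table 2 therefore contains serious events only. The last two rows of the table above are events that the outcome requires and the rule excludes.

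**Step 2. Check the SSI rates used below.** Section 15.3 gives 30% on placebo, a 15-point absolute reduction (so 15% on flucloxacillin), two-sided alpha 0.05, 90% power and 15% loss. With pooled variance under the null and no continuity correction:

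n per arm = [1.960 × √(2 × 0.225 × 0.775) + 1.282 × √(0.30 × 0.70 + 0.15 × 0.85)]² / 0.15² = 160.8, rounded up to 161.

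Total 322; 322 / 0.85 = 379, against 380 stated. The planning rates are read correctly. The protocol gives no figure for the adverse-event outcome itself.

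**Step 3. What would the recorded outcome show if SSI is counted?** Assumptions: SSI counts as an adverse event; the SAE rate s is equal in both arms and independent of SSI; s runs from 1% to 5%, because the protocol gives no SAE rate.

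Recorded proportion = 1 − (1 − SSI rate)(1 − s). Share of counted participants who have an SSI, both arms together = (0.30 + 0.15) / (sum of the two recorded proportions).

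| s | Placebo | Flucloxacillin | Difference (points) | Share with SSI |
|---|---|---|---|---|
| 1% | 1 − 0.70 × 0.99 = 30.7% | 1 − 0.85 × 0.99 = 15.8% | −14.9 | 97% |
| 3% | 1 − 0.70 × 0.97 = 32.1% | 1 − 0.85 × 0.97 = 17.5% | −14.6 | 91% |
| 5% | 1 − 0.70 × 0.95 = 33.5% | 1 − 0.85 × 0.95 = 19.3% | −14.3 | 85% |

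The difference is almost the −15 points of the primary outcome.

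**Step 4. Would recording non-serious events be enough without excluding SSI?** Illustration only, with assumed non-serious rates of 10% on placebo and 25% on flucloxacillin, and s = 2%.

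- Recorded, SSI excluded: 1 − 0.98 × 0.90 = 11.8% against 1 − 0.98 × 0.75 = 26.5%.
- Recorded, SSI included: 1 − 0.70 × 0.98 × 0.90 = 38.3% against 1 − 0.85 × 0.98 × 0.75 = 37.5%.

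An excess of about 15 points in drug-related harm would be cancelled by the SSI benefit. The exclusion of SSI therefore needs to be stated whichever recording rule is chosen.

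**The case against.** The best defence is that limited recording is a deliberate and reasonable choice. Section 14.5.1 gives its reason, a marketed product with extensive safety data, and Section 6.1 classes the trial as Type A, with risk no higher than standard care. That stands as a reason to collect less. It does not rescue an objective and outcome that require what is not collected, but it does mean that narrowing the outcome is as legitimate a repair as widening the collection.

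Three stronger readings are tempting, and the protocol does not support them.

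- A reader might infer that adverse events cannot be measured at all, or that every non-serious event is lost. SAEs are still captured on their own form, side effects are asked about and noted in the diary, and Sections 10.5, 11.1 and 11.2 point towards collection. What is established is a conflict, and the lack of a CRF route if Section 14.5.1 prevails.
- A reader might infer that the safety outcome simply repeats the efficacy outcome. No section says that SSI counts towards it. The exception in Section 14.5.1 may imply this, or may only acknowledge that SSI has its own structured form (Section 11, SSI diagnosis). The figures in Step 3 are conditional on that reading and on rare SAEs.
- A reader might see a gap at 3 months, because "SARs (such as long-term side effects of trial treatment under investigation) should continue to be reported until the end of follow up" while that contact has no adverse-event item. This is a duty to report once a site becomes aware of a reaction. It does not require a scheduled question, and sites still contact participants at 3 months, so it is not an error.

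**Conclusion.** The conflict is real. Sections 5.2, 5.5, 10.5, 11.1 and 11.2 cannot all be met alongside Section 14.5.1 and Table 2, row 11. If Section 14.5.1 is followed, the secondary outcome as worded cannot be produced, and this conclusion needs no numerical assumption.

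The size of any distortion is conditional. If SSI is counted as an adverse event, the planning SSI rates hold, and SAEs are equally frequent in both arms at 1% to 5% (an assumption), the comparison would be about 31-34% against 16-19%, with 85% to 97% of counted participants having an SSI. If SSI is not counted, the recorded outcome reduces to serious events.

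The primary outcome, the sample size and the reporting of SAEs and SUSARs are unaffected.

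**What to change.** Reconcile the sections in one of two ways.

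(a) Amend Section 14.5.1 and Table 2, row 11, so that non-serious adverse events, or at least non-serious suspected reactions, are entered on the CRF at the existing day 5-10, 15-20 and 30 contacts. If only suspected reactions are taken, reword the objective and outcome to match. The cost is a protocol amendment, a CRF change, some extra data entry at calls already planned, and MedDRA coding.

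(b) Keep the limited recording and restate the objective and outcome (Synopsis, Sections 5.2 and 5.5) as SAEs and SARs only, with Sections 10.5, 11.1 and 11.2 brought into line. The cost is an amendment to wording. The trial then makes no claim about non-serious side effects.

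In both cases, define the safety outcome as excluding SSI and report SSI as efficacy. The choice should be made early, because side effects that were not entered may not be recoverable later.
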